1. INTRODUCTION

1.1 MEDICAL BACKGROUND

Back pain is a very common disorder with a point prevalence of approximately 35% in Germany [P11-08387]. In most cases specific causes cannot be identified (i.e. "unspecific low back pain"). Usually, low back pain is a self-limiting disorder, and approximately 90% of patients experience remission within 6 weeks. Musculoskeletal pain in the back area is worsened through a vicious circle of excessive muscle (force) load inducing pain (by minor muscle injury and local muscle ischaemia) that causes non-physiological posture, which in turn causes further pain.

Neck pain is becoming increasingly common throughout the world. The point prevalence of neck pain ranges from 0.4% to 41.5% (mean: 14.4%); and 1 year prevalence ranges from 4.8% to 79.5% (mean: 25.8%). Prevalence is generally higher in women, higher in highincome countries compared with low- and middle-income countries and higher in urban areas compared with rural areas [R12-4817]. Much neck pain is not attributable to a specific disease or disorder and is labelled as "soft-tissue" rheumatism or muscular/ mechanical/ postural neck pain [R15-2389].

Acute back/ neck pain is often treated with over the counter (OTC) analgesics, such as paracetamol, ibuprofen, or naproxen. Other treatment options are local heat [P11-08754] and hyperaemisation inducing agents [R11-2672]. Local heat and hyperaemisation inducing treatment were shown to augment blood flow and haemoglobin oxygenation in the skin and in the muscles [R11-2636, P11-05079]. Thus, such treatments can be assumed to be beneficial in the treatment of such musculoskeletal conditions.

Remedies against acute back/ neck pain, especially in an OTC environment, are required to reduce back discomfort fast and effectively while being tolerated well.

NSAIDs have been used since decades for the treatment of back and neck pain. A systematic review concluded that NSAIDs are effective for short-term symptomatic relief in patients with acute and chronic low back pain without sciatica. However, effect sizes are small [P08-09510]. In a recent review [P15-04711] topical options for the treatment of back/neck pain has been discussed. In a clinical trial a hyperaemisation inducing agent has been shown to reduce back/neck pain with low incidence of side effects [P11-00252].

Topically applied remedies seem to have a low potential for systemic side effects and interactions with other (including systemic) medications.

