The study will be conducted at approximately 20 study centres in Germany and Russia. The trial will end with completion of the last follow-up call (Visit 7T) with the last patient. For a graphical representation of the trial, see Figure 3.1: 1.

c03317678-02

Page 18 of 69

Proprietary confidential information © 2016 Boehringer Ingelheim International GmbH or one or more of its affiliated companies

[figure not shown]

Figure 3.1: 1 Trial design, R = randomisation

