3.3.1 Main diagnosis for trial entry

Only patients with acute neck or back pain will be screened for suitability for the study.

Please refer to Section 8.3.1 (Source Documents) for the documentation requirements pertaining to the in- and exclusion criteria.

3.3.2 **Inclusion criteria**

- 1. Signed and dated written informed consent at Visit 1 in accordance with Good Clinical Practice (GCP) and local legislation.
- 2. Male or female patients ≥ 18 years with current diagnosis of acute back pain or of neck pain for at least 24 hours, but less than 21 days.
- 3. Acute back pain or acute neck pain resulting in pain on movement (POM) \geq 50 mm (VAS 0-100) for at least one POM procedure out of 5 standardized procedures.

The POM measurement with the highest pain response will determine if the patient has back or neck pain (see Section 5.2.1 for further details).

- 4. Sensitivity to algometric pressure on the painful trigger point < 25 N/cm² (see Section 5.2.2).
- 5. Women of childbearing potential* must be ready and able to use highly effective methods of birth control per ICH M3(R2) that result in a low failure rate of less than 1% per year when used consistently and correctly. A list of contraception methods meeting these criteria is provided in the patient information.
 - *Women of childbearing potential are defined as:

Any female who has experienced menarche and does not meet the criteria for "women not of childbearing potential" as described below.

Women not of childbearing potential are defined as:

Women who are postmenopausal (12 months with no menses without an alternative medical cause) or who are permanently sterilized (e.g. tubal occlusion, hysterectomy, bilateral oophorectomy or bilateral salpingectomy).

c03317678-02 Page 21 of 69

Proprietary confidential information © 2016 Boehringer Ingelheim International GmbH or one or more of its affiliated companies

3.3.3 **Exclusion criteria**

- 1. History of 3 or more episodes of back or neck pain in the last 6 months excluding the current episode
- 2. Surgery due to back or neck pain or rehabilitation due to back or neck pain in the last 12 months
- 3. Back or neck pain that is attributable to any specific identifiable cause (e.g. disc prolapse, spondylolisthesis, osteomalacia, inflammatory arthritis, metabolic, neurological diseases or tumour).
- 4. Trauma or strains of the back or neck muscles within the last 3 months.

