7.3.1 Primary endpoint analyses

The primary endpoint 'Change in POM_{WP} between baseline (before application at Visit 1) and Visit 3 (Day 2 evening, 1 hour after application)' will be analysed utilising a restricted maximum likelihood (REML) based repeated measures approach, using all available longitudinal POM_{WP} observations at the assessment times T1 = Visit 1 (Day 1 morning, 1 hour after application), T3 = Visit 2 (Day 2, morning, 1 hour after application, T4 = Visit 3 (Day 2 evening, before application) and T5 = Visit 3 (Day 2 evening, 1 hour after application). The statistical model will be applied to the analysis of change from baseline (T0 = Visit 1 morning, before application) in POM_{WP} at times T1, T3, T4 and T5. The statistical model will include the fixed, categorical effects of treatment, country, application site (back/neck), time and treatment-by-time interaction, as well as the continuous, fixed covariates of baseline POM_{WP} and baseline-by-time interaction. The definition of baseline POM_{WP} is given in Section 7.1.

An unstructured covariance structure will be used to model the within-patient errors. In case this analysis fails to converge, other covariance structures to be employed will include Compound Symmetry, Autoregressive Model, AR (1) and Spatial Covariance, with the covariance structure converging to the best fit, as determined by Akaike's information criterion, to be used for purposes of comparing treatment effects. The Kenward-Roger approximation will be used to estimate the denominator degrees of freedom [R11-1488].

Differences between the treatment group effects (diclofenac/capsaicin - diclofenac, diclofenac/capsaicin - capsaicin, diclofenac/capsaicin - placebo) with regard to the change in POM_{WP} between T0 and T5, calculated as ' POM_{WP} at time T0 - POM_{WP} at time T5' (see Section 5.1) will be estimated by reference to the adjusted least square means and the corresponding 95% confidence intervals (CI). All statistical testing will be performed using a two-sided, alpha = 0.05 level of significance.

The primary analysis will be based on the full analysis set (FAS) as defined in Section 7.3.

In addition to the primary analysis, a separate analysis will be performed to test the heterogeneity of the strata 'application site' and 'country', respectively. In these models the two interaction terms treatment-by-stratum-by- time and stratum-by-time will be added to the primary model, respectively.

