6.3 PATIENT SETS ANALYSED

The patient sets of treated set (TS), full analysis set (FAS) defined in the CTP will be used

The randomised set is defined as all randomised patients, whether treated or not.

Patients having received the wrong treatment will be analysed within the planned (randomised) treatment group in the efficacy analysis (TS as randomized) and within the actual treatment group in the safety analysis (TS as treated).

Patients who are incorrectly randomised into the stratum not containing the POM_{WP} will be included in the patient set TS as randomised but will be allotted to the stratum with the POM_{WP} for efficacy analyses.

Table 6.3: 1 shows which analysis set is used for each class of endpoint.

Table 6.3: 1Patient sets for planned analyses

Planned analysis	Patient set
Disposition	Enrolled patients
Analysis sets	Randomised set
IPVs, demographic and other baseline characteristics, concomitant therapies and treatment compliance	TS (as randomised)
Efficacy analysis: primary, secondary	TS (as randomized) FAS (primary endpoint only)
Safety analysis	TS (as treated)

Note that the number of patients with available data may differ between endpoints. For details, see Section 6.6 "Handling of missing data".

6.5 **POOLING OF CENTRES**

Country will be included in the statistical models therefore no pooling of centres is planned.

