7.1 DEMOGRAPHIC AND OTHER BASELINE CHARACTERISTICS

Descriptive statistics will be presented for the treated set for the following demographic and baseline characteristics, by treatment group and all patients combined:

Demographic data

- Age [years]
- Age class (≥ 18 to $< 65, \geq 65$ years)
- Age class (≥18 to <65, 65 to <85, ≥85 years) (required only for the 'Disposition of patients for data disclosure by age groups' table)
- Sex (Male, Female)
- Race (American Indian/Alaska Native, Asian, Black/African American, Hawaiian/Pacific Islander, White)

• Ethnicity (Not Hispanic/Latino, Hispanic/Latino)

Baseline disease characteristics

- Time since onset of acute pain (days)
- POM (each assessment and POM_{WP})
- $PA[N/cm^2]$
- Pain intensity at rest
- Average pain intensity

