7.4 PRIMARY ENDPOINTS

7.4.1 Primary analysis

The primary endpoint will be analysed as described in the CTP, using the FAS.

Differences between the combination treatment (diclofenac and capsaicin) and individual treatments or placebo will be estimated at visit 3 (day 2 evening, 1 h after application), differences should be calculated as the combination treatment minus the individual treatment or placebo, meaning negative differences favour the combination treatment. Adjusted least squares means (with standard errors) as well as treatment contrasts and their 95% confidence intervals (CIs) and two-sided (α =0.05) p-values will be presented.

The SAS code to be used for this analysis is given in section 9.1.

In addition, the primary endpoint will be summarized by treatment group using descriptive statistics.

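### The primary model and the AUC analyses leave out time since pain onset, a listed baseline value that could add precision at almost no cost

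*Protocol*

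**What the plan says.** Protocol 7.3.1 sets out the primary model in full. On the categorical side, "The statistical model will include the fixed, categorical effects of treatment, country, application site (back/neck), time and treatment-by-time interaction". The continuous part is given as "as well as the continuous, fixed covariates of baseline" POM_WP and the baseline-by-time interaction. SAP 7.4.1 keeps this: "The primary endpoint will be analysed as described in the CTP, using the FAS". Protocol 7.3.2 gives POM_WP AUC72 and AUC120 an ANCOVA with treatment, country, application site and baseline POM_WP, and SAP 7.5.1 refers back to it.

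Time since onset appears elsewhere. Inclusion criterion 2 (Protocol 3.3.2) requires the pain to have lasted "for at least 24 hours, but less than 21 days". SAP 7.1 lists "Time since onset of acute pain (days") among the baseline disease characteristics to be summarised. On the natural course, Protocol 1.1 says that "low back pain is a self-limiting disorder, and approximately 90% of patients experience remission within 6 weeks". Protocol 3.2 applies the self-limiting description to both back and neck pain when it explains the choice of the Day 2 evening time point.

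On centres, Protocol 3.1 says "The study will be conducted at approximately 20 study centres in Germany and Russia", and SAP 6.5 says "Country will be included in the statistical models therefore no pooling of centres is planned".

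**The concern.** Patients enter at very different points of an illness that resolves by itself. Someone one day into an episode and someone twenty days into it may be expected to change by different amounts over the next day and a half, whichever gel they use. A covariate measured before randomisation that predicts part of this change would narrow the confidence intervals without affecting the validity of the comparison. The plan expects to have this value but does not use it in the primary or key secondary models.

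The precision matters most in one place. Protocol 7.2 requires all three contrasts to be significant. The contrast with placebo has 70 evaluable patients in the smaller arm and is the weakest of the three, so residual variance there has the largest effect on the chance of success.

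**Working it through.** **Inputs.** Protocol 7.7: difference 12 mm, common SD 30 mm, two-sided 0.05, 210 evaluable patients in each active arm and 70 on placebo. The share of residual variance that onset would explain (R²) is not in the documents. It is an assumption, shown over a range.

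**1. Reproduce the plan's figures.** SE = 30 × √(1/n₁ + 1/n₂); power ≈ Φ(12/SE − 1.96).

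- Combination vs each single component: SE = 30 × √(2/210) = 2.93 mm; power 98.4% (noncentral t 98.3%). The plan says 98%.
- Combination vs placebo: SE = 30 × √(1/210 + 1/70) = 4.14 mm; power 82.6% (noncentral t 82.3%). The plan says 82%.
- Smallest significant difference, 1.96 × SE: 5.74 mm and 8.12 mm. The plan says 5.7 and 8.1 mm.

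**2. Add a covariate.** Replace the SD with 30 × √(1 − R²) and recompute with the noncentral t distribution. The last column is the chance of winning all three contrasts when each true difference is 12 mm. It was simulated with a shared combination arm (400,000 runs).

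| Assumed R² | SD (mm) | Power vs each component | Power vs placebo | All three |
|---|---|---|---|---|
| 0 | 30.00 | 98.3% | 82.3% | 81.0% |
| 1% | 29.85 | 98.4% | 82.7% | 81.4% |
| 5% | 29.24 | 98.7% | 84.2% | 83.2% |
| 10% | 28.46 | 99.1% | 86.1% | 85.4% |

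In terms of sample size, 700/(1 − R²) gives 707, 737 and 778. The gain is therefore equivalent to about 7, 37 or 78 more evaluable patients.

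**3. Cost in degrees of freedom.** The primary model covers four post-baseline times (T1, T3, T4, T5). Onset with its time interaction means four time-specific slopes, hence about four degrees of freedom. Each ANCOVA needs one. Neither matters with about 700 patients.

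**4. What the existing terms already remove.** The time effect takes out average recovery. Country takes out the mean difference between Germany and Russia. Baseline POM_WP may carry part of any onset effect. R² above refers only to what is left after these.

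**The case against.** The strongest case is that nothing here is wrong. The model contains both stratification factors and the baseline value of the outcome, and randomisation makes the contrasts valid without more. That stands: this is an improvement, not the repair of an error.

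The size is assumed. No section links onset to change over about 36 hours. The six-week remission figure is for low back pain and says little about a day and a half, and Protocol 3.2 chose an early time point partly so that spontaneous recovery would not shrink the treatment difference. This also stands, although that choice protects the difference between arms and does not remove variation between patients. At R² of 1% the gain is under half a percentage point.

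The starting power is uncertain too. Protocol 7.7 does not say whether 30 mm is net of covariates. If the single components beat placebo, the placebo difference would exceed 12 mm; at an assumed 15 mm, Φ(15/4.14 − 1.96) is about 95%, leaving little to gain. A straight line in days may also be the wrong shape, but that would only recover less variance and would not bias the comparison.

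A reader might go further and infer that all natural recovery stays in the error term. It does not, for the reasons in step 4 of the working. A reader might also infer that centre must be in the primary model, because a two-level country term cannot absorb differences among about 20 centres. The premise is fair but the conclusion does not follow. Patients rate POM themselves, Protocol 5.2.1 requires the same trained person to support each patient's assessments, and the endpoint is change from baseline, so a stable site effect largely cancels. A random centre term that is dropped on non-convergence would add a data-dependent step to a model that already has a covariance fallback.

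**Conclusion.** The omission is confirmed for the primary model and for both AUC analyses. Its consequence is a possible loss of precision only. Under an assumed 1% to 10% of residual variance explained, power against placebo moves from about 82% to between 83% and 86%, and the contrasts with the single components gain less than one percentage point. If onset has no prognostic value, adding it gains nothing and costs almost nothing.

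This rests on the plan's 12 mm and 30 mm and on reading 30 mm as the residual SD of the planned model. That onset will be available for essentially every patient is inferred from the inclusion criterion and the SAP baseline table; neither document states it. The SAS code (SAP 9.1) is not in the public text, but SAP 7.4.1 ties the primary analysis to the protocol model. The documents do not support a reading that the planned analysis is biased or that its error rate is wrong.

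**What to change.** In the SAP, before unblinding:

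- Add time since onset (days, continuous) and its interaction with time to the primary repeated-measures model.
- Add time since onset as a covariate to the AUC72 and AUC120 ANCOVAs.
- State a rule for missing onset, such as the overall mean across all arms, so that no patient drops out of the model. SAP 6.6.2 currently rules out imputing baseline data, so it needs an explicit exception.
- Record the change from Protocol 7.3.1 and 7.3.2 in SAP section 4.

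A centre-within-country random effect is optional. If wanted, it belongs in a sensitivity analysis and not in the primary model.

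The cost is SAP wording and code, plus the few degrees of freedom counted above. No new data collection is foreseen, given that SAP 7.1 already plans to report onset in days.

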7.3.2 Secondary endpoint analyses

The key secondary and other secondary endpoints will be analysed with the treated set as defined for efficacy analysis in Section 7.3.

The key secondary endpoints of $POM_{WP}AUC_{72}$ and $POM_{WP}AUC_{120}$ will be analysed using an analysis of covariance (ANCOVA) including treatment, country and application site (back/neck) as fixed effects and the baseline POM_{WP} as a continuous covariate. Treatment differences will be estimated by reference to the adjusted least square means and the corresponding 95% confidence intervals. The statistical testing will be performed using a two-sided, alpha = 0.05 level of significance.

The number of patients with a decrease in POM_{WP} of at least 30% from baseline until Day 2 evening, 1 hour after drug application, will be analysed by a logistic regression model, adjusting for the categorical covariates country and application site (back/neck). The likelihood-ratio test will be used to test for differences between treatments. Adjusted odds ratios together with 95% confidence intervals will be used to quantify the effect of treatment, comparing all treatments to the treatment of diclofenac/capsaicin as the reference treatment.

The number of patients with a decrease in POM_{WP} of at least 50% from baseline until Day 2 evening, 1h after drug application, will be analysed correspondingly.

The change in POM_{WP} between baseline and the morning of Day 6 will be analysed analogously to the primary endpoint. The statistical model will be applied to the analysis of change from baseline (T0 = Visit 1 morning, before application) in POM_{WP} at times T1, T3, T4, T5 and - additionally at times T7 (=Visit 4 = Day 3 morning, 1 hour after application), T9 (= Visit 5 = Day 4 morning, 1 hour after application) and T12 (= Visit 6 = morning of Day 6).

The change in PA between baseline and Day 2 evening, before drug application (Visit 3) will be analysed analogously to the primary endpoint using all available longitudinal PA observations at the assessment times T2 = Visit 2 (Day 2 morning, before application) and T4 = Visit 3 (Day 2, evening, before application). The statistical model will be applied to the analysis of change from baseline (T0 = Visit 1 morning, before application) in PA at times T2 and T4.

The change in PA between baseline and the morning of Day 6 will be analysed analogously to the primary endpoint. The statistical model will be applied to the analysis of change from

Page 50 of 69

Proprietary confidential information © 2016 Boehringer Ingelheim International GmbH or one or more of its affiliated companies

baseline (T0 = Visit 1 morning, before application) in PA at times T2, T4, T6, T8 and additionally - T12 (= Visit 6 = morning of Day 6).

c03317678-02 Trial Protocol Page 51 of 69

c03317678-02 Page 52 of 69

Proprietary confidential information © 2016 Boehringer Ingelheim International GmbH or one or more of its affiliated companies

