7. STATISTICAL METHODS AND DETERMINATION OF SAMPLE SIZE

7.1 STATISTICAL DESIGN - MODEL

This is a randomized, double-blind, placebo- and active-controlled, multi-country, multi-centre 4-arm parallel group study to investigate efficacy and tolerability of multiple doses of a topically applied combination containing diclofenac 2% + capsaicin 0.075% (2 g formulation per application; 2-times daily for 5 days (-1/+2 days) compared to placebo, as well as to diclofenac 2% and capsaicin 0.075% in patients with acute back or neck pain.

The patients will be randomised via IRT in blocks to the treatment groups diclofenac + capsaicin, diclofenac, capsaicin and placebo in a 3:3:3:1 ratio. Treatment allocation will be stratified by country and the application site (back or neck) of the study drug; the application site is classified after the POM assessments on a 0-100 mm VAS, following the 5 standard procedures, before application at Visit 1 as that site, where the worst pain is identified, and the corresponding POM is then denoted as POM_{WP}. Post-dose POM_{WP} and POM assessments for the other procedures within the corresponding stratum (back or neck) will be captured each with the same scale and the same standard procedure, respectively. For further details of POM assessments see Section 5.2.1.

Based upon these design considerations, the trial will be analysed using general linear models which will include terms for treatment, country (Germany or Russia), application site (back or neck) and the baseline POM_{WP} as continuous covariate.

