7.5.2.1 Endpoints from POM_{WP}

The number of patients with a decrease in POM_{WP} of at least 30% from baseline until day 2 evening, 1h after drug application, will be analysed using a logistic regression model as described in the CTP. Treatment differences will be analysed using adjusted odds ratios which will be presented together with 95% confidence intervals, the combination treatment (diclofenac and capsaicin) will be used as the reference treatment. Odds ratios will be

[figure not shown]
calculated as combination treatment/individual treatments or placebo, meaning an odds ratio >1 would indicate better responses for the combination treatment.

The number of patients with a decrease in POM_{WP} of at least 50% from baseline until day 2 evening, 1h after drug application, will be analysed similarly.

Change in POM_{WP} between baseline and the morning of day 6 will be analysed analogously to the primary endpoint, using all available data points as described in CTP section 7.3.2.

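### The 30% and 50% responder models adjust for country and application site but not for baseline POM_WP; adding it is a small, free improvement

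*Protocol*

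**What the plan says.** Protocol 7.3.2 specifies a logistic regression for the 30% responder endpoint, "adjusting for the categorical covariates country and application site (back/neck", with a likelihood-ratio test for treatment. The 50% endpoint at Day 2 "evening, 1h after drug application, will be analysed correspondingly". SAP 7.5.2.1 says the 30% endpoint "will be analysed using a logistic regression model as described in the CTP", treats the 50% endpoint similarly, and adds no covariate.

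The models for the more important pain endpoints do use baseline pain:

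- Primary repeated-measures model (protocol 7.3.1): "the continuous, fixed covariates of baseline POM_{WP} and baseline-by-time interaction".
- AUC72 and AUC120 ANCOVAs (protocol 7.3.2): country and site "as fixed effects and the baseline POM_{WP} as a continuous covariate".

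Protocol 7.1 sets out the general approach: "the trial will be analysed using general linear models". Besides treatment and country, the terms it lists are "application site (back or neck) and the baseline POM_{WP} as continuous covariate". The available text gives no reason for leaving baseline out of the responder models. Protocol 7.2 makes these endpoints supportive only.

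**The concern.** The responder endpoints are meant to support the primary result, yet they are adjusted differently from it. Using a percentage fall does not by itself deal with baseline. If the reduction does not scale with baseline, the chance of being a responder still depends on starting pain, upwards or downwards. Randomisation is stratified by country and application site only (protocol 7.6), so baseline pain can differ between arms by chance, most of all against placebo with its 70 evaluable patients.

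What is at stake is some precision, and how the odds ratios read beside the primary result. If the two disagreed, nobody could tell at once whether the different adjustment was the cause.

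**Working it through.** **1. The plan's own figures.** No power is stated for the responder endpoints. The primary figures in protocol 7.7 (12 mm, SD 30 mm, two-sided 0.05) reproduce:

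- 210 vs 210: SE = 30 × √(2/210) = 2.93 mm; 12/2.93 = 4.10; power = Φ(4.10 − 1.96) = 98.4% (stated 98%).
- 210 vs 70: SE = 30 × √(1/210 + 1/70) = 4.14 mm; 12/4.14 = 2.90; power = Φ(2.90 − 1.96) = 82.6% (stated 82%).

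This point does not affect them.

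**2. Does a percentage threshold remove baseline?** Assumptions not in the documents: a control patient with baseline B has mean reduction 20 + s(B − 70) mm, with slope s from 0 to 1. The residual SD is √(900 − (12s)²), which keeps the overall SD near the protocol's 30 mm. A responder at fraction k needs a reduction of at least kB, so

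P(response) = Φ([20 + s(B − 70) − kB] / SD).

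The numerator changes by s − k per mm of baseline. In this model the dependence vanishes only when s = k.

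| k | s | SD (mm) | P at B = 50 mm | P at B = 100 mm |
|---|---|---|---|---|
| 30% | 0 | 30.0 | Φ(5/30) = 57% | Φ(−10/30) = 37% |
| 30% | 0.3 | 29.8 | Φ(−1/29.8) = 49% | Φ(−1/29.8) = 49% |
| 30% | 1.0 | 27.5 | Φ(−15/27.5) = 29% | Φ(20/27.5) = 77% |
| 50% | 0 | 30.0 | Φ(−5/30) = 43% | Φ(−30/30) = 16% |
| 50% | 0.5 | 29.4 | Φ(−15/29.4) = 30% | Φ(−15/29.4) = 30% |
| 50% | 1.0 | 27.5 | Φ(−25/27.5) = 18% | Φ(0) = 50% |

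The direction depends on an unknown slope, and no single slope clears both thresholds. In simulation the responder odds ratio per 10 mm of baseline ran from about 0.85 to 1.45 (30%) and 0.76 to 1.32 (50%).

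**3. Power with and without baseline.** 1,000 simulated trials per setting, 210 vs 210, effect 12 mm, baseline truncated normal on 50 to 100 mm (location 70, scale 14), likelihood-ratio test at 0.05:

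| Slope s | 30%: without → with | 50%: without → with |
|---|---|---|
| 0 | 88.0 → 88.3% | 87.1 → 87.8% |
| 0.3 | 91.5 → 91.1% | 89.2 → 89.1% |
| 0.5 | 91.2 → 91.7% | 89.3 → 89.4% |
| 0.8 | 92.3 → 92.8% | 91.5 → 91.7% |
| 1.0 | 91.8 → 93.1% | 92.4 → 93.0% |

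The largest gain is 1.3 points. Type I error was about 4% to 6% either way. The largest change in odds ratio was 1.97 to 2.04, about 4%. Power near 90% leaves little room for gain. With effects of 9 to 11 mm and 2,500 runs per setting, the change was about −0.4 to +3.3 points: clearly positive where response depends on baseline, about zero where it does not.

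**4. Chance imbalance, 210 vs 70.** The assumed baseline distribution has SD about 11.4 mm, so the chance difference between arms has SE = 11.4 × √(1/210 + 1/70) = 1.6 mm. At an odds ratio of 1.45 per 10 mm, a 1.6 mm imbalance shifts the log odds ratio by 0.16 × ln 1.45 = 0.06. The standard error of the treatment log odds ratio is about 0.28 to 0.30, so the shift is about a fifth of it. At 0.76 per 10 mm the shift is 0.16 × ln 0.76 = −0.04. Without the covariate, the correlation between imbalance and the estimated effect reached about 0.2 in size; with it, about 0.

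**The case against.** The case for leaving the models alone is strong on several counts, and most of it stands.

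- **Section 7.1.** A reader might infer that the responder models contradict it. The documents do not support that strictly. The sentence speaks of general linear models, which logistic regression is not, and 7.3.2 is the specific rule, clear and executable as written.
- **Room to improve.** A reader might argue that patients with more pain have more room to improve. That fits absolute change, not a percentage threshold: at 30%, a 50 mm patient needs 15 mm and a 100 mm patient needs 30 mm, and either can fall by 100%. The argument that survives is the one about scaling in step 2.
- **Validity.** A reader might infer a biased or invalid test. Randomisation protects the unadjusted test, and the simulated type I error agrees.
- **The placebo comparison.** A reader might expect a serious distortion there. In simulation, adding baseline moved the log odds ratio with an SD of about 0.02 to 0.06, well under its standard error, and changed power by −0.8 to +2.4 points.
- **Completeness.** That every other pain analysis adjusts for baseline can be said only of those visible in the public text. The SAP's SAS code section is not included.
- **Availability.** The treated set, used for these endpoints, does not formally require a baseline, and SAP 6.6.2 does not impute one. This is no obstacle: without a baseline no percentage decrease can be calculated.

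None of this gives a reason to prefer the model without baseline.

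**Conclusion.** The point holds as a minor improvement. Both responder models omit a prognostic covariate that is measured in every patient by design and already used in the primary and key secondary pain models. The expected benefit is about 0 to 3 points of power, plus an odds ratio that no longer moves with chance baseline imbalance. These sizes rest on assumptions outside the documents: the baseline distribution, a control reduction of 20 mm and slopes of 0 to 1. The smaller effects of 9 to 11 mm are also assumed; the 30 mm SD and 12 mm effect are the protocol's. If response happens not to depend on baseline, the gain is nil and the cost negligible. No confirmatory conclusion is affected.

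**What to change.** In protocol 7.3.2 and SAP 7.5.2.1, add baseline POM_WP as a continuous covariate to the 30% and 50% responder logistic models, beside treatment, country and application site. If the sponsor prefers to leave it out, one sentence giving the reason would do.

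The cost is one term in two models. No new data are needed, and no patient who can be classified as responder or non-responder is lost. The odds ratio becomes conditional on baseline and may sit slightly further from 1 (at most about 4% in the simulations); it is already conditional on country and application site. Fixing the choice in advance avoids a later choice between adjusted and unadjusted results.
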